8.4 Effectiveness Analysis Methods

8.4.1 Analysis of Primary Endpoint

Change in crestal bone level between implant loading and 12 months post-loading will be measured as the primary endpoint. Crestal bone levels on both the mesial and distal aspect of the implant will be considered and the mean of the two measurements will be used as the primary endpoint. If only one of the two measurements is available, the available measurement will be used in the analysis. The hypothesis tested is described in Section 8.1.

Mean change in crestal bone level between treatment groups will be compared via a one-sided t-test. If assumptions of normality are violated, an appropriate non-parametric method or data transformation will be sought.

Additional summaries with subjects categorized into one of the following groups based on the change in crestal bone level: bone gain, no change, 0 to <1 mm loss, 1 mm to <2 mm loss, 2 mm to <3 mm loss, and ≥3 mm loss will be presented.

Summary statistics of the primary endpoint will be presented for raw values and change from baseline overall and by study center. If it is believed that the primary endpoint results may be affected by study center, ANCOVA methods may be used with treatment assignment as main effect and study center as a covariate. Other covariates, including implant site, implant length, racial data, age, gender, history of tobacco use, controlled diabetes, full-mouth plaque score, simultaneous grafting may also be added as covariates in the exploratory analyses.

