3.4 Primary Endpoint

Mean crestal bone level change from implant loading to 12 months post-implant loading will be measured as the primary endpoint. Crestal bone levels on both the mesial and distal aspect of the implant will be averaged to calculate the crestal bone level.

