8.1 Sample Size

The following assumptions were used to determine the sample size for the primary endpoint of mean change in crestal bone level between implant placement and 12 months postimplant loading:

- Subjects will be assigned to either the test or control treatment group
- The primary analysis is a non-inferiority comparison of the test treatment to the control treatment

- The standard deviation for both test and control treatments is 0.5 mm
- A difference between treatment groups of ≥ 0.5 mm is considered clinically significant (i.e., the non-inferiority margin)
- The difference between the treatment groups is expected to be 0 mm
- Greater than 80% power is considered sufficient
- Statistical test will be performed with a one-sided 5% significance level

The hypotheses associated with the primary endpoint are defined as follows:

$$H_0$$
: $\mu_c \ge \mu_s + \delta$

$$H_1$$
: $\mu_c < \mu_s + \delta$

where μ_c is the mean change in crestal bone level for the test implants, μ_s is the mean change in crestal bone level for control implants, and δ is the pre-defined non-inferiority margin of 0.5 mm. The study will be considered successful if the null hypothesis is rejected, i.e., the conclusion of non-inferiority is achieved. If non-inferiority is achieved at a one-sided α of 5%, a one-side superiority test will be performed at significance level of 5%.

To maintain at least 80% power to detect a difference between treatment groups of 0.5 mm with a common standard deviation of 0.5 mm, 14 subjects per treatment group would be required for a total of 28 subjects. Adjusting for potential 25% attrition, 19 subjects per treatment group will be required for a total of 38 subjects. An additional 14 subjects will be enrolled in order to provide more data for the implant success and survival calculations, thereby bringing the total sample size to 52.

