10.3.1	Pooling Across Centers	10
10.3.2	Pooling Across Protocol Versions at Enrollment	10
10.4	HANDLING OF MISSING DATA.....	11
10.5	OTHER DATA SUMMARIES.....	11
10.6	CHANGES TO PLANNED ANALYSES	11
10.7	STATISTICAL SOFTWARE	11

1 Purpose of the Statistical Analysis Plan

The purpose of this Statistical Analysis Plan (SAP) is to summarize the statistical methodologies being used to confirm the primary effectiveness endpoint and assess the secondary effectiveness, additional effectiveness, and safety endpoints of the immediate implantation of the Straumann® Bone Level Tapered Implant (study device). The SAP will be used should there be any discrepancies with the protocol.

2 Study Design

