4.4 Safety Endpoints

The safety endpoints are defined as the number of adverse events or adverse device effects experienced and the number and proportion of subjects experiencing an adverse event or adverse device effect throughout the study.

5 Analysis of Primary Effectiveness Endpoint

The primary effectiveness endpoint evaluates the difference in the change in mean crestal bone levels from implant loading to 12 months post-implant loading between the treatment and control groups. The change is defined as the mean crestal bone level of the mesial and distal aspects of the implant at 12

months post-implant loading minus at implant loading and the difference is defined as the change for the treatment group minus the control group.

The mean crestal bone levels at each visit, and the change in mean crestal bone levels will be summarized for each group with the count, average, standard deviation, median, minimum, and maximum. The mean change in crestal bone levels will also be categorized as Gain (>0), No change (0), Loss <1 mm, Loss <2 mm, Loss <3 mm, or loss ≥ 3 mm and summarized with the number and proportion of subjects in each category for each treatment group.

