10.4 Handling of Missing Data

All practical monitoring and follow-up steps will be taken to ensure complete and accurate data collection. All analyses will be based on available data only; no imputation for missing data is planned.

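### The one-aspect rule for crestal bone level does not require the same aspect at loading and at 12 months, so a stable mesial-distal gap can be counted as bone change

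*Protocol*

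**What the plan says.** Protocol section 3.4 forms a single level per visit: "Crestal bone levels on both the mesial and distal aspect of the implant will be averaged to calculate the crestal bone level". Section 8.4.1 then covers an unreadable aspect: "If only one of the two measurements is available, the available measurement will be used in the analysis". It does not say that the aspect used at one visit must also be the one used at the other.

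SAP section 5 fixes the order of operations. It states "The change is defined as the mean crestal bone level of the mesial and distal aspects of the implant at 12" and continues "months post-implant loading minus at implant loading and the difference is defined as the change for the treatment group minus the control group". The two aspects are therefore averaged within a visit, and the visit means are subtracted afterwards.

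The SAP has no rule for a visit with one reading. Its only statement on missing data, in section 10.4, is "All analyses will be based on available data only; no imputation for missing data is planned". SAP section 1 sets precedence: "The SAP will be used should there be any discrepancies with the protocol".

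**The concern.** Averaging first and subtracting second is harmless when both aspects are read at both visits. It is also harmless when the same aspect is missing at both. When an aspect is read at one visit only, a one-aspect level is compared with a two-aspect mean, and any standing difference in height between the mesial and distal bone enters the change score although no bone has moved.

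That score feeds the primary non-inferiority test, the gain/no change/loss categories in SAP section 5 (where no change means exactly 0), and the test for pooling protocol versions in SAP section 10.3.2. A one-aspect loading value would also carry into the 24- to 60-month changes, because SAP section 4.3 measures all of them from loading.

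**Working it through.** **Inputs from the documents.** Margin 0.5 mm, SD of change 0.5 mm in each group, expected difference 0 mm, one-sided 5% level and at least 80% power (protocol 8.1, SAP 5.1); 46 of 53 randomized subjects completed 12 months (SAP 2.1). **Assumed, because the documents give no figure:** the mesial-distal gap, the share of subjects mismatched, and an even split of completers (23 per arm).

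**Planned sample size.** With a noncentral t, 13 per group gives 79.7% power and 14 gives 82.4%, so the stated 14 is reproduced. 14/(1 − 0.25) = 18.7, rounded up to 19 per group and 38 in total, also as stated.

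**Error for one subject.** Let M and D be the mesial and distal levels, with 0 for loading and 12 for 12 months. The two-aspect change is (M12 + D12)/2 − (M0 + D0)/2.

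- Mesial unread at 12 months only: derived value D12 − (M0 + D0)/2; error (D12 − M12)/2, half the 12-month gap.
- Mesial unread at loading only: derived value (M12 + D12)/2 − D0; error (M0 − D0)/2, half the loading gap.
- Mesial unread at 12 months and distal unread at loading: derived value D12 − M0; error (D12 − M12)/2 + (D0 − M0)/2, which is the whole gap if it is stable.
- Same aspect unread at both visits: no mismatch.

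With a stable gap and no true change, assumed gaps of 0.2, 0.5 and 1.0 mm give false changes of 0.10, 0.25 and 0.50 mm. Example: M = 0.8 and D = 0.2 at both visits, with distal unread at 12 months, gives 0.8 − 0.5 = 0.30 mm. Using the mesial aspect at both visits gives 0.

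**Effect on the trial if mismatch is unrelated to arm.** For share f mismatched at one visit and a mean-zero gap with SD s, the SD of change becomes √(0.25 + f·s²/4).

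| s (mm) | f | SD of change (mm) | Power, 23 per arm | Power, 14 per arm |
|---|---|---|---|---|
| – | 0 | 0.500 | 95.5% | 82.4% |
| 0.3 | 5% | 0.501 | 95.4% | 82.3% |
| 0.5 | 10% | 0.506 | 95.1% | 81.6% |
| 1.0 | 20% | 0.548 | 92.0% | 76.0% |

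**Effect if mismatch differs by arm and the gap is systematic.** Bias = excess share × gap/2. The last column is the one-sided type I error at the margin, with 23 per arm and SD 0.5 mm, if the bias favours the test arm.

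| Gap (mm) | Excess share in one arm | Bias (mm) | Type I error |
|---|---|---|---|
| 0.2 | 5% | 0.005 | 5.4% |
| 0.5 | 10% | 0.025 | 7.0% |
| 1.0 | 20% | 0.10 | 16.4% |

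**Error left by the aspect-matched rule.** With mesial unread at 12 months, the matched value D12 − D0 differs from the two-aspect change by half the change in the gap between visits. If the gap has mean zero, the same variance σ² at both visits and between-visit correlation ρ, this error has variance σ²(1 − ρ)/2, against σ²/4 under the present rule. Matching is more precise when ρ exceeds 0.5.

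**The case against.** Section 8.4.1 introduces the endpoint as a change and then speaks of averaging two measurements. Read alone, it could mean that two aspect-level changes are averaged, which would avoid the mismatch. That reading does not fit protocol 3.4 or SAP section 5, both of which average levels.

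The SAP takes precedence, defines change from both aspects and plans no imputation, so a visit with one reading might simply count as missing. A reader might instead infer that the SAP confirms the one-aspect rule. It does neither expressly, and the point is unsettled. That is a further reason to write the derivation down.

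The radiographs are standardized with a stent and the same holder and aiming device (protocol 5.2.5), and one blinded central reader measures them (5.2.6). This may make unread aspects rarer, but it does not correct a mismatch. Section 5.2.6 leaves measurement detail to an operations manual that is not among the documents; a rule for unread aspects could be there.

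Two stronger readings are tempting. One is that a 0.5 mm error in a subject uses up the margin. The margin applies to a difference in group means: one subject in 23 with a 0.30 mm error moves the arm mean by 0.30/23 = 0.013 mm, under 3% of 0.5 mm. The other is that a grafted socket wall is harder to read in one arm, so that the comparison is biased. The current protocol requires socket grafting in both arms (3.3, 5.2.3, 6.4), and the version 2 wording described in SAP 10.3.2 did not distinguish the arms either. Mesial and distal losses in similar numbers would also tend to cancel.

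**Conclusion.** The gap in the derivation is real. As written, the plan permits a one-aspect level to be subtracted from a two-aspect mean, and nothing in either document prevents it. The error is half the gap at the visit with the missing reading. It equals half the loading gap only if the gap is stable.

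The likely effect on the trial is small. The protocol foresees one-aspect readings but gives no frequency, and the number is probably low. Under the assumed ranges, mismatch unrelated to arm costs at most 3.5 percentage points of power at 23 per arm (95.5% to 92.0%). The type I error figures show what would follow from a systematic gap together with differential missingness. They are not evidence that either exists. The point is worth settling because the change is cheap and should be made before results are seen. It does not call the sample size or the design into question.

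**What to change.** Add a derivation rule to SAP section 5 through an amended SAP approved before the primary analysis, the route in SAP section 10.6:

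- Compute change separately for the mesial and distal aspects, as 12 months minus loading, using only aspects read at both visits.
- Average the available aspect changes. A subject with one such aspect contributes that aspect's change.
- Treat a subject with no aspect read at both visits as missing.
- Apply the same rule at 24, 36, 48 and 60 months.
- Report the number of one-aspect subjects by arm.

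Subjects with both aspects at both visits keep exactly the planned value, and the sample size is unchanged. There are two costs. The rare subject with opposite aspects missing becomes missing. A one-aspect change also still stands in for the two-aspect mean, so the gain in precision depends on the gap being reasonably stable between visits (correlation above about 0.5 under the conditions set out in the working). The documents give no figure for that correlation.

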8.4.2 Analysis of Secondary Endpoints

All secondary effectiveness endpoints will be summarized descriptively and no hypothesis tests are planned. Secondary endpoints include implant success and survival rates, implant stability as measured by RFA, dimensional changes of the buccal bone as measured on CBCT images, changes in soft tissue measurements (gingival and papilla margins – baseline at final restoration), and subject satisfaction (esthetics, function, and level of pain).

8.4.3 Analysis of Additional Endpoints

Additional effectiveness measures will be collected at 24-, 36-, 48-, and 60-months post implant loading. These endpoints will be summarized descriptively and no hypothesis testing is planned. The additional endpoints include implant success and survival rates, dimensional changes of the buccal bone as measured on CBCT images, changes in soft tissue measurements (gingival and papilla margins – baseline at final restoration), and subject satisfaction (esthetics, function, and level of pain)..

8.4.4 Analysis of Safety Endpoints

For analysis of safety endpoints, summary tables and/or listings will be provided for all adverse events by event category. Adverse events will also be summarized by relationship to the study device, implant procedure, by seriousness, severity and by outcome. Adverse events leading to discontinuation from the study will be tabulated. Except where indicated, a subject reporting the same adverse event more than once will be counted once when calculating the number and percentage of subjects with that particular event. Except where indicated, if a subject reports the same adverse event more than once, the strongest relationship to the procedure and/or device recorded for the event will be presented.

Adverse events that occurred in screen failure subjects will be presented separately.

8.5 General Statistical Methods

A qualified statistician using validated statistical software will perform all statistical analyses. Unless otherwise specified, the data will be summarized for non-missing subjects in tables listing the mean, standard deviation, minimum, maximum, and number of subjects in a group of continuous data, or number of subjects and percentage in each category for categorical data, as appropriate. In general the denominator for the percentage calculation will be based upon the total number of subjects (N) in the study population for the treatment groups, unless otherwise specified.

All the statistical tests will be based on a 2-sided test at the significance level of 0.05, unless otherwise specified.

8.5.1 Balance in Baseline Characteristics

To assess balance in baseline characteristics, the distribution of each baseline variable of interest will be compared between the two treatment groups. Continuous variables will be summarized using mean, median, standard deviation, 95% confidence interval, and range; testing between the two groups will be based on a two-sample t-test (or Wilcoxon rank-sum test as appropriate). Categorical variables will be summarized using counts and percentages, and differences between treatment groups will be assessed using a Chi-square test (or Fisher's exact test as appropriate).

All baseline demographic variables and other characteristics (including history of tobacco use, oral situation (number of missing teeth, natural teeth and number of implants), reason for tooth extraction/loss, modified sulcus bleeding index, pocket probing depths at 6 sites on adjacent teeth, and oral hygiene) will be summarized by treatment group.

8.5.2 Surgery and Supporting Procedures

Summaries of select surgery and other supportive measures will be presented by treatment group.

Detailed information regarding the surgical procedure will be presented in listings. This will include information on crestal bone measurements, bone quality, evaluation of primary stability, guided bone regeneration, and soft tissue procedures.

Details regarding other supportive procedures in the study will be presented in listings, including suture removal, second stage surgery, soft tissue procedures, impressions, temporary prosthesis placement, and final prosthesis placement.

8.5.3 Other Data Summaries

Concomitant medications will be presented in listings and also summarized by drug category. Protocol deviations will be summarized by deviation type and study center.

8.5.4 Subject Disposition

A detailed description of subject disposition will be provided by study group using a CONSORT diagram and summaries of subjects falling in various subgroups of interest,

such as enrolled but did not receive study treatment and early withdrawals. All enrolled (i.e., randomized) subjects entered in the study will be accounted for in the summary.

8.5.5 Missing Data

Every effort will be made to minimize the amount of missing data. If a subject drops out of the study prior to completing their primary endpoint assessment, every effort will be made to measure their primary endpoint immediately prior to discontinuation if possible.

The primary effectiveness measure of change in crestal bone level will be based on available data. Sensitivity analyses based on last observation carried forward will be performed if missing data of the primary endpoint exceeds 10%. Other techniques for sensitivity may be explored.

If standard statistical tests or clinical review indicate the presence of outliers for the primary endpoint, an additional analysis excluding such outliers will also be performed and the rationale for such exclusion will be described completely.

9 Data Management

The general data management procedures are described below, details can be found in the Data Management Plan.

Required clinical data for this study will be collected and recorded in the clinical database using an electronic case report form for all study subjects from whom informed consent is obtained. Site numbers and subject numbers will be used to track subject information throughout the registry. The Principal Investigator or authorized designee is responsible for the timely completion and electronic signature of all electronic case report forms. The information entered into the database will be checked systematically by the data management for inconsistent, illogical and/or missing data using electronic and manual validation checks defined in the Data Validation Plan. If validation of data leads to discrepancies, data management will generate electronic queries. The timely resolution of the queries is under the responsibility of the monitor and the investigators at site. The query process is an ongoing process starting with the first data entered into the database.

The electronic clinical data system used for this study has a security system that prevents unauthorized access to the data and any deletion of data (audit and edit trail).

10 Study Management

10.1 Regulatory and Ethical Requirements

10.1.1 Informed Consent

Informed consent will be obtained from all subjects prior to study participation as described in Section 4.1.1.

10.1.2 Institutional Review Board

Prior to initiation of any study procedures, the protocol and informed consent will be submitted to an IRB for review and approval. In addition, any amendments to the protocol or informed consent will be reviewed and approved (if necessary) by the IRB. The sponsor must receive a letter documenting the IRB approval at the center prior to the initiation of the study at the center.

The investigator is responsible for providing the appropriate reports to the IRB during the course of the clinical study. This will include the following:

- Informing the IRB of the study progress periodically as required, but at a minimum annually
- Reporting any unanticipated serious adverse device effects within 10 working days of becoming aware of the event
- Reporting any deviations from the protocol that adversely affect the risk/benefit
 ratio, the rights, safety, or welfare of the participants, or integrity of the study
- Providing any other reports requested by the IRB

10.2 Reports and Record Management

10.2.1 Investigator Records

The following will be required from the investigator prior to the initiation of the study:

- A signed confidentiality agreement
- Signed and dated curriculum vitae of the investigator(s) and a copy of his/her dental license
- Signed financial disclosure
- A signed copy of the final protocol and any amendments
- A signed copy of the clinical study agreement with the sponsor
- IRB approval letter and IRB approved informed consent document

10.2.2 Case Report Forms

The investigator will be responsible for the accuracy of the data entered on the Electronic Case Report Forms (eCRFs). The investigator will also allow a Straumann representative and/or regulatory bodies to review the data reported on the case report form with the source documents as far as is permitted by local regulations.

10.2.3 Source Documents

Source documents are defined as the original point of entry of a specific data point. Source documents will include, but are not limited to, progress notes, electronic data, computer printouts, radiographs, and recorded data from automated instruments. All source documents pertaining to this study will be maintained by the investigator and made available for inspection by authorized persons.

10.2.4 Records/Data Retention

Original radiographs, photographs, and study documents will be maintained at the research center in a file established for this study. All study documentation needs to be stored at the research center for at least fifteen (15) years following the completion of the study, as specified by the sponsor. The investigator should have access to the study documents in order to answer any queries associated with the study. All other study records will be kept by Straumann once the study has been completed. These records will be maintained at Straumann according to Straumann standard operating procedures.

